In addition to the above industry-initiated studies, the Lake Washington Vascular VenaSeal™ Post-Market Evaluation (WAVES) study was a single-center multiple-investigator, single-arm prospective study investigating the use of the VenaSeal™ system in patients with symptomatic VRD. The study assessed the use of the VenaSeal™ system in GSVs (n=48), SSVs (n=8), and accessory saphenous veins (n=14).³¹ Diseased veins of up to 20 mm diameter were included. The WAVES protocol did not allow adjunctive tributary treatment at the time of the index procedure which were staged at 3 months post-index procedure.

There were 70 veins treated in 50 subjects. All primary target veins (48 GSV, 14 ASV, and 8 SSV) showed 100% closure using DUS at 7 days and 1 month. Complete closure at 3 months was achieved in 70 (99%) of the treated veins. By 3 months, the revised Venous Clinical Severity Score (rVCSS) (6.5 ± 2.4 at baseline to 1.8 ± 1.4 at 1 month and 3 month; p<0.001), Aberdeen Varicose Vein Questionnaire (AVVQ) (17.3 ± 7.9 at baseline to 8.9 ± 6.6 at 1 month and 6.5 ± 7.2 at 3 month; p<0.001), and the EQ VAS (84 ± 12 at baseline to 88.3 ± 8.7 at 1 month and 88.6 ± 10.6 at 3 month; p = 0.002) all showed statistical improvement between baseline and 1 month, and baseline and 3 month visits. The percentage of patients who required adjunctive treatments at three months was lower than had been predicted by the treating physicians (65% versus 96%, p=.0002).³² Procedural pain was mild with a Nominal Pain Rating (NPR) of 2.2 ± 1.8, and the mean time to return to work and normal activities was 0.2 ± 1.1 and 2.4 ± 4.1 days, respectively.

Phlebitis was the most common AE, occurring in the treatment area or side branches in 10 patients (20%), but resolving in all but one subject (2%) by one month. One patient developed body hives within the first week of the procedure which was resolved following antihistamine and steroid treatment, this was said to be consistent with a cyanoacrylate allergy. There were no DVTs or other SAEs. One patient had a thrombus extension at the seven-day DUS which was no longer evident at the one-month DUS. Between the 1-month and 3-month visits, there was one AE, knee bursitis in the treatment limb which was determined as unrelated to the procedure.³²

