10.2. Scheduled Follow-up Visit Windows

The target visit dates for the subject that gets enrolled in the study can be obtained via 'Visit Scheme' CRF from the study database. Should a subject miss a visit or if the visit falls outside of the pre-specified window, a study deviation must be reported, and the original follow-up schedule should be maintained for subsequent visits.

Data analyses include follow-up visits, regardless of whether the visit occurs within the window. Therefore, a late visit is preferred over a missed visit but must be accompanied by a deviation report. Follow-up visit windows are listed in **Table 8** and **Table 9** and are based on days post-procedure.

Table 8: Follow-up Visit Window – All Subjects, VenaSeal vs Surgical Stripping Study will follow this schedule to 12 months

Study Follow-up Visit	Window (Calculated days post index procedure)		
	Window Start (days post- procedure)	Target (days post- procedure)	Window End (days post- procedure)
Day 7	5	7	9
Day 30	23	30	37
6 Months	154	182	210
12 Months	309	365	421
24 Months	674	730	786
36 Months	1039	1095	1151
48 Months	1404	1460	1516
60 Months	1769	1825	1881

Table 9: Additional Follow-up Visit Window – VLU Study

Study Follow-up Visit	Window (Calculated days post index procedure)		
	Window Start (days post-procedure)	Target (days post-procedure)	Window End (days post-procedure)
2 Months	53	60	67
3 Months	83	90	97
4 Months	113	120	127
5 Months	143	150	157
8 Months	226	240	254
10 Month	286	300	314

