Post-index procedure, DUS evaluation is required to assess target vein (including primary target vein) closure after VenaSeal™ system or ETA treatment and absence of refluxing vein or residual vein after surgical stripping. DUS is also used for thrombus assessment. This DUS assessment will also be performed at 7 days, 30 days, 6, 12, 24, 36, 48 and 60 months. This DUS assessment could be completed on the day of the follow-up visit or anytime during the follow-up visit window, as applicable to the site's standard scheduling process.

Patient-Reported Symptoms

Subjects will be asked to report symptoms related to their target limb: pain, aching, itching, burning, sensitivity, heaviness and swelling, and asked to identify their dominant symptom from this list. This will be assessed at baseline and at follow-up visits through 12 months. These questions must be completed by the subject and a translation will be available in each of the applicable languages; however, designated site staff may verbally read the symptom list to the patient.

Venous Treatment Satisfaction Questionnaire (VenousTSQ)

The two components of the VenousTSQ are evaluated as two separate primary endpoints in this study. The questionnaire needs to be completed either by the subject or by a delegated person who asks the questions to the subject and completes the questionnaire on behalf of the subject. This should be the first subject-reported assessment at all study visits when administered.

The Venous Treatment Satisfaction Questionnaire (VenousTSQ) is a new Patient Reported Outcome Measure (PROM). Via a qualitative design approach involving patient interviews and clinical expert reviews, the process resulted in an independently developed tool for venous patients. The tool consists of two components, the peri-procedural early component of treatment satisfaction which will be measured at 30 days post index-procedure (VenousTSQe), and the longer-term status component of treatment satisfaction which can be measured at 30 days, 6 and 12 months (VenousTSQs). Questions focus on topics relevant for patients with varicose veins who have undergone a venous treatment and include items on treatment satisfaction/dissatisfaction, symptoms such as pain, and outcome satisfaction/dissatisfaction.

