7.5 Adjustments for Multiple Comparisons

In the randomized studies, Hochberg procedure will be used in the adjustments for multiple comparisons on primary and key secondary endpoints (Benjamini & Hochberg, 1995)¹. Familywise type I error 0.05 will be used for the primary endpoints and type I error preserved from the primary endpoints will be used for the key secondary endpoints.

VenaSeal vs. ETA Randomized Study

In each randomized study, p-values for the primary endpoints will be ordered from largest to smallest as $p_{p1} > p_{p2} > p_{p3}$ from the 3 hypothesis tests H_{p1}, H_{p2} and H_{p3} , and for the key secondary objectives in descending order as $p_{s1} > p_{s2}$ from the 2 hypothesis tests for key secondary endpoints H_{s1} and H_{s2} , the procedure is as follows:

Step 1. If $p_{p1} < \alpha$, then claim success on all 3 hypotheses for primary endpoints H_{p1}, H_{p2} and H_{p3} ; and proceed to Step 1a, otherwise, go to step 2.	
Step 1a. If $p_{s1} < \alpha$, then claim success on both hypotheses for key secondary endpoints H_{s1} and H_{s2}; otherwise, go to step 1b.
 
Step 1b. If $p_{s2} < \alpha/2$, then claim success on hypothesis for key secondary endpoint H_{s2}; otherwise, both hypotheses for key secondary endpoints H_{s1} and H_{s2} are unsuccessful

Step 2. If $p_{p2} < \alpha/2$, then claim success on two hypotheses for primary endpoints H_{p2} and H_{p3} ; and proceed to Step 2a, otherwise, go to step 3.	
Step 2a. If $p_{s1} < \alpha/2$, then claim success on both hypotheses for key secondary endpoints H_{s1} and H_{s2}; otherwise, go to step 2b.
 
Step 2b. If $p_{s2} < \alpha/4$, then claim success on hypothesis for key secondary endpoint H_{s2}; otherwise, both hypotheses for key secondary endpoints H_{s1} and H_{s2} are unsuccessful

Step 3. If $p_{p3} < \alpha/3$, then claim success on hypothesis for primary endpoint H_{p3} ; and proceed to Step 3a, otherwise, no success on all 3 hypotheses for primary endpoints H_{p1}, H_{p2} and H_{p3}	
Step 3a. If $p_{s1} < \alpha/3$, then claim success on both hypotheses for key secondary endpoints H_{s1} and H_{s2}; otherwise, go to step 3b.
 
Step 3b. If $p_{s2} < \alpha/6$, then claim success on hypothesis for key secondary endpoint H_{s2}; otherwise, both hypotheses for key secondary endpoints H_{s1} and H_{s2} are unsuccessful

$\alpha = 0.05$ for Endothermal Ablation (ETA) study.	

VenaSeal vs. Surgical Stripping Randomized Study

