7.9.1.2 Analysis of Key Secondary Endpoints

7.9.1.2.1 Hypothesis

For key secondary endpoint of return to work, the following hypothesis will be tested:

$$H_0: S_A(t) = S_C(t)$$

$$H_a: S_A(t) \neq S_C(t)$$

Where $S_A(t)$ and $S_C(t)$ are the survival functions for freedom from return to work for the VenaSeal™ system arm and ETA or surgical stripping arm, respectively.

For the other key secondary endpoint of primary target vein closure rate at 6 months, the following hypothesis will be tested:

$$H_0: S_A(t) \leq S_C(t) - 10\%$$

$$H_a: S_A(t) > S_C(t) - 10\%$$

Where $t = 6$ months, and $S_A(t)$ and $S_C(t)$ are the survival functions for freedom from vessel re-opening at 6 months in the VenaSeal™ system arm and the ETA or surgical stripping arm, respectively and -10% is the non-inferiority margin.

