7.9.1.2.2 Endpoint Definition

Return to work is defined as the time in days patients need following a procedure to return to work. Employment status will be captured for all patients. Only patients who have an active employment status (employed or independent worker, including stay at home parents) will be included in the analysis for return-to-work time. Information will be captured on the category of occupation to be able to distinguish between physical and sedentary work. Patients will be censored at the time of study exit.

The other key secondary endpoint to be assessed is the primary target vein closure rate after index treatment. The primary target vein should be the saphenous vein (GSV, SSV, accessory saphenous veins) which at the investigator's discretion is most likely responsible for the greatest portion of the patient's symptoms or pathology. This vein will be treated first.

For subjects treated with the VenaSeal™ system or ETA, anatomic closure of the primary target vein is defined as Doppler ultrasound (DUS) showing primary target vein closure along the entire treated vein segment with no discrete segments of patency exceeding 5 cm. Any areas with >5 cm patency will be measured, and information will be collected on the location of the patency, length of the patency (cm), diameter of the patency (mm), the presence of flow (Y/N), the presence of reflux (Y/N), and the presence of thrombus (Y/N). For subjects treated with surgical stripping, anatomic closure of the primary target vein is defined as the absence of clinically significant refluxing truncal vein incompetency and no discrete segments of patency exceeding 5 cm in the primary target vein. Any areas with vein remnants will be measured and information will be collected on the location of the remnant, length of the remnant (cm), the presence of flow (Y/N), the presence of reflux (Y/N), and the presence of thrombus (Y/N). Lack of anatomic closure on the date of the index procedure will not be considered relevant to this endpoint, since some treatments may not achieve closure immediately.

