7.9.1.2.4 Analysis Methods

For the return to work endpoint, a Kaplan-Meier survival estimator will be used to estimate the survival functions for both the VenaSeal™ and the control arm (i.e., ETA or Surgical Stripping). Day zero is the date of the index procedure. The censoring time is the time to study exit, the later of either the last contact date or the discontinuation date, or the time point for analysis, whichever comes first. A cumulative incidence figure will be produced to compare the two treatments. A log-rank test will be used to test whether the survival distributions differ between the treatment groups. If a patient is reported to have returned to work, but the date of return is unknown, the return date will be imputed from the date of the follow-up visit. For those who have returned to work, the median, Q1, Q3, minimum, and maximum will summarize the number of days to return to work, as well as the number who have not returned to work in each treatment arm.

The treatment effect for primary target vein closure at 6 months, one of the key secondary endpoints, is the difference in the survival curves at time t for each randomized study. A Kaplan-Meier survival estimator will be used to estimate each curve. Day zero is the date of the index procedure. The censoring time is the time to last study visit (scheduled or unscheduled), the time point for analysis, or time to exit, whichever comes first. The non-inferiority test for treatment (VenaSeal) versus control (ETA or Surgical Stripping) will be performed using the test statistic proposed in da Silva, Logan and Klein (2009)³. The Z test statistic will calculate $S_A(t) - S_C(t) + 0.10$ for the numerator where t is at 6 months and the square root of the sum of the Greenwood's variance estimators for each of $S_A(t)$ and $S_C(t)$ in the denominator.

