7.9.1.6 Healthcare utilization secondary endpoints

The following healthcare utilization secondary endpoint data will be collected for both of the CEAP 2-5 Randomized Studies:

1. Rate of adjunctive treatments conducted through 12 months post-index procedure.

Hypothesis

There is no formal hypothesis test for this study objective.

Endpoint Definition

Rate of adjunctive procedures, phlebectomy or sclerotherapy, for varicosity on the target limb through 12 months post index procedure.

Analysis Methods

The number and rate of adjunctive procedures through 12 months will be estimated by study arm. To calculate the rate, the numerator is the count of adjunctive procedures. The denominator is the number of person-years of follow-up. The amount of follow-up per person is defined as their date of exit or last known follow-up or the date of their 12 month follow-up visit (whichever is first) minus their date of index procedure. A similar estimate will be constructed for the type of adjunctive procedure, phlebectomy or sclerotherapy.

Determination of Subjects for Analysis

The analysis will consist of the ITT population.

2. Healthcare utilization related to the target limb Venous Reflux Disease (VRD), as determined by the number of healthcare visits conducted, between study visits through 60 months (through 12 months for VenaSeal vs. Surgical Stripping Study).

Hypothesis

The following hypothesis will be tested:

$$H_0: r_A = r_C$$

$$H_a: r_A \neq r_C$$

Where r_A and r_C are the rates of healthcare utilization in the VenaSeal™ system arm and the ETA or surgical stripping arm, respectively.

Endpoint Definition

Rate of healthcare utilization visits related to venous reflux disease.

Analysis Methods

The number and rate of healthcare utilization visits will be estimated by study arm. To calculate the rate, the numerator is the count of HCU visits. The denominator is the number of person-years of follow-up. The amount of follow-up per person is defined as their date of exit or last known follow-up minus their date of index procedure. A similar estimate will be constructed within the HCU type of interest (Inpatient, Outpatient, Clinic, Outpatient ER visits).

Determination of Subjects for Analysis

The analysis will consist of the ITT population.

3. Procedures, tests, and treatment of AEs related to the treatment modality or index procedure through 60 months (through 12 months for VenaSeal vs. Surgical Stripping Study).

Hypothesis

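### The 6-month closure non-inferiority test gives no day for its analysis time and no rule placing the day 154–210 ultrasound at that time, so late-seen re-openings can be counted as closed

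*SAP*

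**What the plan says.** SAP 7.9.1.2.1 states the closure hypothesis in terms of quantities that "are the survival functions for freedom from vessel re-opening at 6 months", with a 10-point margin. SAP 7.9.1.2.4 sets day zero at the index procedure and censors at "the time to last study visit (scheduled or unscheduled), the time point for analysis, or time to exit, whichever comes first". The test statistic is S_A(t) − S_C(t) + 0.10 over the root of the summed Greenwood variances, with t described only as 6 months. SAP 7.9.1.2.2 adds: "Lack of anatomic closure on the date of the index procedure will not be considered relevant to this endpoint". Scans at day 7 and day 30 therefore count.

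The scan schedule is in the protocol. Table 8 in section 10.2 gives the 6-month visit a target of day 182 and a window of days 154 to 210. Section 10.5 says: "This DUS assessment could be completed on the day of the follow-up visit or anytime during the follow-up visit window". Section 10.2 also says: "Data analyses include follow-up visits, regardless of whether the visit occurs within the window".

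The SAP version history records that version 3.0 moved closure to a time-to-first-event analysis. The sample size in SAP 6.1.2 still assumes closure proportions compared with a Farrington-Manning score test.

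**The concern.** Re-opening can be found only at an ultrasound, so its recorded date depends on when the scan was booked. A curve read at a fixed day near 182, with events at actual scan dates, ignores every re-opening first found on days 183 to 210. Those veins are censored at t as closed. No difference in timing between the arms is needed: removing the same fraction of failures from both curves shrinks an absolute deficit towards zero, which is the direction that favours non-inferiority.

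This is one of two key secondary tests under error control; SAP 7.5 states that "type I error preserved from the primary endpoints will be used for the key secondary endpoints". As written, the false-positive rate of the closure test depends on site scheduling and on a visit-mapping choice left to programming in an open-label trial.

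**Working it through.** **The plan's own figure.** Inputs from SAP 6.1.2: 95% against 95.4%, margin 10 points, one-sided 0.0167, 80% power, 1:1, 10% attrition. The Farrington-Manning score formula gives 118.3, so 119 per arm (power 80.3%), and 238/0.9 = 264.4 against the stated 264. For stripping the asymptotic formula gives 46 per arm against the stated 44; exact power at 44 is 83.7%. The sample sizes are not in dispute.

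**Hand calculation.** Assumptions not in the documents: t = day 182, re-opening dated by the scan, 6-month scans uniform over days 154–210, later visits in the data, and failures first seen either at day 30 or at the 6-month scan. The window holds 210 − 154 + 1 = 57 days, of which 28 fall after day 182. At the margin (85.4% against 95.4%) the deficit the curves show is

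10 × (1 − share × 28/57),

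where share is the fraction of failures first seen at the 6-month scan. This gives 6.6 points for 70%, 7.5 for 50% and 8.8 for 25%. Simulation gave 6.7, 7.8 and 9.1. At 70% the curves read 90.2% and 96.9%.

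**False non-inferiority at the margin.** SAP Z test, 132 per arm, 10% attrition, one-sided 0.0167, uniform scans, later visits in the data, 6,000 to 15,000 simulated trials per scenario:

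| Share first seen at 6-month scan | t = 182, actual scan dates |
|---|---|
| 90% | 31% |
| 70% | 18–19% |
| 50% | 9–10% |
| 25% | 4% |
| 10% | 2.5% |

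With scans placed at the nominal day the rate is 2.1–2.7% over shares from 25% to 90%. That is the baseline of this test, slightly above 0.0167 because of the Greenwood variance.

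**Scan timing and follow-up** (70% / 25% share). Non-uniform scan days are normal with SD 10, limited to 154–210.

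| 6-month scan days | Later visits in data | Data end at 6-month visit |
|---|---|---|
| Centred on 190 | 47% / 6% | 43% / 6% |
| Uniform | 18–19% / 4% | 8% / 3% |
| Centred on 182 | 18% / 3.5% | not run |
| Centred on 174 | 5.0% / 2.4% | 0.9% / 1.3% |
| Centred on 168 | 3.6% / 2.1% | 0.2% / 0.7% |

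The error is near nominal if all scans fall on or before t (2.0%) or if the between-arm excess is seen by day 30 (1.9%).

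**Other levels in SAP 7.5** (uniform scans, later visits, 70% / 25%): 31% / 10% at 0.05, 22% / 6% at 0.025, 12–14% / 2% at 0.0083.

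**Stripping study** (54 per arm, 74.8% against 84.8%, later visits): 6% / 3%, against 1.8–2.0% with nominal-day mapping.

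**Choice of t** (70% share). Day 180 or 183 instead of 182 gives 20% or 17%. Day 210 gives 2.3% when later visits are in the data. If the data end at the 6-month visit, closed subjects leave the risk set at their own scan and the curves at day 210 read 58% and 85% for true values of 85.4% and 95.4%.

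**Evidence on the share.** In the single-centre WAVES cohort all primary target veins "showed 100% closure using DUS at 7 days and 1 month" (protocol 4.1), and SAP Table 2 lists 98.0% at 6 months, so its failures were first seen after day 30. That is one or two failures, too few to set the share; 98.0% is also not an attainable count out of the listed 70 (68/70 = 97.1%, 69/70 = 98.6%).

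**The case against.** The strongest reply is that the harmful reading is nowhere written. The protocol analyses visits whether or not they fall in the window, allows the scan at any point in it, and describes closure as a 6-month measurement. That points to by-visit counting, under which the error is about nominal. The point about intent stands. However, the protocol sentence keeps a day-195 scan in the data without placing it at or before t, and the written Kaplan-Meier rule does not do so either. For adjunctive treatments the SAP does set a visit-based cut-off, "or the date of their 12 month follow-up visit (whichever is first) minus their date of index procedure". That defines a person-time denominator, so it is suggestive rather than decisive.

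Three further points stand. The size is not determined by the documents: at the one level of 0.0167 the two tables above run from 0.2% to 47%. Part of each figure is the test's own baseline of about 2%, so the timing effect at a 25% share is only about two points. The null is also remote, since every VenaSeal 6-month rate in SAP Table 2 is 90.3% or higher. None of these removes the bias.

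Mapping scans to the nominal day also has a cost in meaning: a re-opening first seen well after the window counts as a 6-month failure, and unscheduled scans need their own dating rule. These rules should be written down.

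**Conclusion.** The concern holds and should be fixed before the closure analysis is run. The gap in the text and the direction under the ordinary reading (t near day 182, events dated by scan) are clear. The size is conditional. With uniform scans and later visits in the data, false non-inferiority at a nominal 0.0167 is about 18–19% at a 70% late-seen share and 4% at 25%, against a baseline of 2.1–2.7%. It is larger if sites scan late, and near nominal or conservative if they scan early. These are error rates at the margin, not forecasts of the trial's result. It is more than a missing detail, because naming a day (182 or 210) while keeping actual scan dates can still give a wrong answer; what matters is the visit mapping. The descriptive closure estimates use the same rule but carry no hypothesis test.

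**What to change.** Keep the Kaplan-Meier analysis and add to SAP 7.9.1.2.4:

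- Each scheduled ultrasound, including one outside its window, takes the nominal day of its visit for both re-opening and censoring.
- The day for t is stated so that the 6-month scan counts at t; day 182 does this once scans are mapped.
- Rules are given for a missing 6-month scan and for re-openings found at earlier or unscheduled visits.

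Do not simply move t to day 210: that works only when later visits are in the data, and it misses scans after the window. Closure status at the 6-month visit with the Farrington-Manning test, which matches the sample-size calculation, can serve as a sensitivity analysis. Apply the same mapping to the descriptive closure estimates.

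The cost is SAP wording and programming, with no new data, and version 3.0's aim of handling censoring and unscheduled visits is kept. Reported closure rates may be slightly lower. Simulated power at 95% against 95.4% falls from 97% to 91% (70% share) or from 93% to 92% (25% share), still above the planned 80%.
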